### **3.2 Secondary objective(s)**

The secondary objectives of this study are to evaluate any biochemical changes in creatine phosphokinase (CPK), sex hormone binding globulin (SHBG), ferritin, angiotensin converting enzyme (ACE) level, and lipid panel, as well as the change in daily LT4 dose in the same population upon switch from conventional tablets to Tirosint capsules.

## **4 TRIAL DESIGN**

This will be an open-label, phase IV study.

Enrolment will be stopped as soon as 48 patients are completed or 60 patients are included in the Tirosint treatment phase, whatever comes first.

Adult patients with a history of hypothyroidism due to total thyroidectomy, who are on stable doses of levothyroxine tablets (between 88 and 250 mcg daily) for at least 6 weeks before screening visit and with a history of gastroesophageal reflux disease (GERD) or associated gastrointestinal issues on prescription (Rx) PPIs (i.e. omeprazole  $\geq$  20 mg daily, or esomeprazole  $\geq$  20 mg daily, or lansoprazole  $\geq$  15 mg daily, or dexlansoprazole  $\geq$  30 mg daily, or pantoprazole  $\geq$  40 mg daily, or rabeprazole  $\geq$  20 mg daily) for at least 8 weeks before screening visit will be included in the study.

During the screening visit, subjects (holding their morning dose of LT4) will undergo screening serum measurements for TFTs (TSH, FT4, free T3 [FT3], total T3 [TT3]), along with a physical examination. Subjects complying with inclusion/exclusion criteria will enter a run-in period, in which they will continue taking their levothyroxine and PPI medications as per prescription, at their current dose. Should the patient require LT4 dose adjustment at screening visit, it will be possible to re-screen the patient until TSH normalization under the new dose.

Four to 6 weeks later (from screening or last re-screening), subjects (fasting and holding their morning dose of LT4) will undergo baseline serum measurements of TSH, FT4, FT3, TT3, as well as total T4 (TT4), creatine phosphokinase (CPK), sex hormone binding globulin (SHBG), ferritin, angiotensin converting enzyme (ACE) level, and lipid panel (triglycerides [TG], total cholesterol [TC], high-density lipoproteins [HDL], low-density lipoprotein [LDL], and very-low-density lipoproteins [VLDL]) as baseline thyroid function related serum laboratory assessments. Patients will then be switched to Tirosint® capsules at the same daily dose.

Patients will remain on Tirosint® for 12 weeks (time frame allowed: 11-13 weeks) and will continue their regular intake of Rx PPI, throughout the whole study duration, according to prescription.

Tirosint® will be taken as a single daily dose in the morning, on an empty stomach, one-half to one hour before breakfast. All subjects will separate their LT4 by at least 4 hours from any drug known to interfere with LT4 absorption (e.g. iron and calcium supplements), and by at least 1 hour from foods that are known to interfere with LT4 absorption.

Halfway through the Tirosint® treatment period (time frame allowed: 5-7 weeks), subjects will report to the clinical center and (holding their morning dose of LT4) will undergo intermediate serum measurements of TSH, FT4, FT3, TT3, for safety assessment.

At the end of the 12 week Tirosint® treatment period, patients will report to the study site for the final visit and (fasting and holding their morning dose of LT4) they will undergo a physical examination, and serum measurements of TSH, FT4, TT4, FT3, TT3, CPK, SHBG, ferritin, ACE level, and lipid panel.

In addition to the laboratory tests, the subjects' safety will be evaluated throughout the study by adverse event monitoring.

#### *Study design and study population*

The study has been designed as a preliminary evaluation in patients, therefore an open-label, non-randomized design has been judged appropriate.

Each patient's control will be the baseline evaluation with their standard therapy.

Thyroidectomized patients have been selected being the endogenous production of thyroid hormones absent; therefore, circulating thyroxine (T4) is of exogenous origin only.

Patients with GERD or associated gastrointestinal issues have been selected as these are common pathologies, which are usually treated with PPIs.

#### *Choice of the doses*

The doses between 88 and 250 mcg have been selected because patients who have had a thyroidectomy are usually treated with dosages above 88 mcg, while patients in treatment with unusually high doses of LT4 (greater than 250 mcg) may have other underlying factors affecting absorption of the drug.

The strengths of omeprazole, esomeprazole, lansoprazole, dexlansoprazole, pantoprazole and rabeprazole have been selected based on the Prescribing Information of the authorized products. Only prescription (Rx) products (either brand or generics) will be accepted, since over-the-counter (OTC) products are authorized only for short-term treatment (not more than 14 days every 4 months), unless directed by the prescribing doctor.

#### *Choice of evaluation parameters and timing for evaluations*

Pharmacological therapy with synthetic levothyroxine is currently monitored and adjusted on the basis of the FT4 and TSH serum levels. TSH is a widely recognized marker of thyroid function status. Therefore it has been selected as primary efficacy outcome and as indicator of LT4 absorption. Additional laboratory tests related to thyroid hormone status will be evaluated.

The peak therapeutic effect of a given dose of levothyroxine may not be attained for 4 to 6 weeks. In adult patients with primary hypothyroidism, it is recommended to monitor serum TSH levels after an interval of 6 to 8 weeks after any change in dose ([IBSA Pharma Inc 2018](#)). Therefore in the study the first (intermediate) visit will be performed 6 weeks after switch to Tirosint, for safety purposes and the final visit will be performed 12 weeks after switch, when TSH is supposed to be stabilized.

### *Patients safety*

The patients will be administered the same pre-screening dose of LT4 according to the approved modalities; therefore no adverse events (AEs) due to LT4 are expected. Moreover, safety checks of TFTs will be performed every 6 weeks upon switch to Tirosint and, should TSH levels > 10 or < 0.01 mIU/L be measured, a dose adjustment will be allowed.

Proton pump inhibitors therapy will also be continued at the same pre-screening dose and as per the prescribed modalities. Therefore, a safety concern is not advised.

### *Pregnancy and breastfeeding*

Experience with levothyroxine use in pregnant women, including data from post-marketing studies, have not reported increased rates of major birth defects or miscarriages, while there are risks to the mother and fetus associated with untreated hypothyroidism in pregnancy. Therefore levothyroxine should not be discontinued during pregnancy. Nevertheless, since TSH levels may increase during pregnancy, TSH should be monitored and levothyroxine dosage adjusted during pregnancy.

There is insufficient information to determine the effects of levothyroxine on the breastfed infant and no available information on the effects of levothyroxine on milk production. The developmental and health benefits of breastfeeding should be considered along with the mother's clinical need for levothyroxine and any potential adverse effects on the breastfed infant from levothyroxine or from the underlying maternal condition (IBSA Pharma Inc 2018).

Regarding PPIs, their safety of use in pregnancy and lactation varies depending on the active ingredient. Nevertheless, there are no adequate and well-controlled studies with each PPI in pregnant women. In addition, at least for some PPIs, harm to the nursing infant cannot be excluded (e.g. [Takeda Pharmaceuticals America Inc. 2017](#)).

Taking in consideration the above information, only non-pregnant and non-lactating females will be included in the study. Should a pregnancy onset after inclusion, the patient will drop out of the study.

## **5 SELECTION OF POPULATION**

### **5.1 Subjects selection**

A maximum number of 60 adult patients will be enrolled in this study, in order to have at least 48 patients completed.

The Clinical Investigator is to give his/her approval to the participation of each subject in the study on the basis of acceptable medical history and findings in the physical examination and laboratory investigations which comply with the inclusion/exclusion criteria below.

## 5.2 Inclusion criteria

Inclusion in the study requires compliance with all the following criteria for inclusion:

- I1. written informed consent duly read, signed and dated by the subject;
- I2. aged  $\geq 18$  and  $\leq 75$  years;
- I3. history of hypothyroidism due to total thyroidectomy;
- I4. on stable LT4 tablet doses for at least 6 weeks at screening ( $\geq 88$  mcg daily and  $\leq 250$  mcg daily);
- I5. TSH at screening  $\geq 0.3$  and  $\leq 4.0$  mIU/L;
- I6. history of gastroesophageal reflux disease or associated gastrointestinal issues on prescription PPIs (i.e. omeprazole  $\geq 20$  mg daily, or esomeprazole  $\geq 20$  mg daily, or lansoprazole  $\geq 15$  mg daily, or dexlansoprazole  $\geq 30$  mg daily, or pantoprazole  $\geq 40$  mg daily, or rabeprazole  $\geq 20$  mg daily) for at least 8 weeks before screening visit and for whom chronic therapy with PPIs for the next 5 months has been prescribed;
- I7. for women, adequate and continuative contraceptive measures until the end of the study, if not in menopause;
- I8. reasonable assumption of understanding the study and willingness to take part to the study and to comply with protocol requirements.

## 5.3 Exclusion criteria

The presence of any of the following criteria for exclusion will mean that the patient is not eligible for inclusion in the study:

- E1. suspected or ascertained non-compliance with LT4 or PPI therapy;
- E2. subject requiring changes of levothyroxine dose;
- E3. use of over-the-counter (OTC) PPIs, unless directed by the prescribing physician;

---

 Should a patient require LT4 dose adjustment at screening visit, it will be possible to re-screen the patient until TSH normalization under the new dose (see also section 7.2). Should a patient require LT4 dose adjustment at baseline visit, the subject will be excluded.

 Use of OTC PPIs will only be allowed if the patient is using an OTC PPI chronically as directed by his/her prescribing physician, and chronic prescription can be appropriately documented (copy of the documentation to be collected and kept in the patient's file)

 Appropriate methods are implants, injectables, combined oral contraceptives, IUDs, sexual abstinence or vasectomised partner.

- E4. history of malabsorption or history of gastric bypass surgery, short-gut syndrome, inflammatory bowel disease and other conditions of the gastrointestinal tract that may affect drug absorption (e.g. celiac disease);
- E5. multiple co-morbidities (e.g. cardiac heart failure, active arrhythmia or history of arrhythmia, particularly atrial fibrillation, uncompensated diabetes mellitus, uncorrected adrenal insufficiency, seriously compromised hepatic, renal and/or respiratory functions);
- E6. neoplastic pathology, active or in remission for less than 5 years (excluding the basic thyroid pathology);
- E7. terminal condition;
- E8. parenteral or assisted enteral feeding;
- E9. presence of any medical condition or other circumstances which would significantly affect the safety of the subject or decrease the chance of obtaining reliable data, achieving study objectives or completing the study;
- E10. history of alcoholism, drug abuse or psychiatric diseases that could invalidate the informed consent or limit the subject compliance with protocol requirements;
- E11. pregnant (positive urine pregnancy test at screening or baseline visits) or breast-feeding subject or subject planning a pregnancy in the next months;
- E12. known hypersensitivity to the ingredients of the preparation involved in the study;
- E13. use of forbidden concomitant medications (see [section 6.5](#));
- E14. regular consumption of soy and soy derivatives, cotton seed meals, walnuts, and dietary fibers;
- E15. participation in other clinical studies during the 3 months prior to screening;
- E16. presumption of poor reliability/cooperation;
- E17. any reason which, in the opinion of the Investigator, would prevent the subject from participating in the study.

#### 5.4 Withdrawal of subjects

Participation may be discontinued for any of the following reasons:

---

 Checked by medical history

- voluntary subject withdrawal for any reason;
- at the Investigator's discretion (reason should be specified);
- if an adverse event (including worsening of concomitant illness) develops, which is considered by the Investigator as incompatible with the continuation of the study;
- if the administration of a drug which is not permitted according to the exclusion criteria is necessary (this should be discussed between the Investigator and the Sponsor);
- failure to comply with the requirements of the protocol or significant protocol deviation (e.g. inclusion error, evidence of non-compliance with exclusion/inclusion criteria arisen during the study, subject misses study visits or/and is not compliant with drugs intake, etc.);
- if a pregnancy develops;
- lost to follow-up;
- patient death;
- if LT4 dose adjustment is required upon receipt of baseline (V2) laboratory results and before any control visit (interim or unscheduled) is performed;
- if PPIs dose adjustment outside the allowed range is necessary or if PPIs are discontinued.

Subjects who withdraw or are withdrawn from the study after inclusion in the Tirosint® treatment phase (V2) will not be replaced. Subjects who withdraw or are withdrawn from the study before inclusion in the Tirosint® treatment phase (during the run-in phase) will be considered as screening failures.

See section 7.4 for the assessments to be performed in case of early withdrawal.

[figure not shown]

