Tirosint® will be taken as a single daily dose in the morning, on an empty stomach, one-half to one hour before breakfast, according to labelling. All subjects will separate their LT4 by at least 4 hours from any drug known to interfere with LT4 absorption (e.g. iron and calcium supplements, see section 6.5) and by at least 1 hour from foods that are known to interfere with LT4 absorption.

The patients will continue intake of PPI according to their individual prescription and habits.

Patients will remain on their pre-screening dose (both for LT4 and for PPI) throughout the whole study duration.

No LT4 dose adjustments will be allowed during the whole study, unless TSH levels > 10 or < 0.01 mIU/L are measured, which require immediate dose adjustment of LT4. In particular:

- If TSH levels > 10 or < 0.01 mIU/L are measured during the baseline visit the subject will drop-out, because pre- and post-switch comparisons at the same dose would not be possible.
- If TSH levels > 10 or < 0.01 mIU/L are measured during control visits (interim or unforeseen), the dose will be adjusted and the subject will remain in the study. To the purpose of the efficacy evaluation in such cases reference is made to section 11.3.

The Investigator can adjust the LT4 dose for a patient with TSH levels < 10 or ≥ 0.01 mIU/L, if this is considered necessary for the safety of a patient. The reason should be appropriately documented.

Changes in the dose of PPI are acceptable during the study provided that the dose remains ≥ 20 mg/day for omeprazole, esomeprazole and rabeprazole, ≥ 15 mg/day for lansoprazole, ≥ 30 mg/day for dexlansoprazole, and ≥ 40 mg/day for pantoprazole. If the newly prescribed dose falls outside this range or if the therapy with PPI is interrupted, the subject will drop out of the study.

Any changes will be described in the CRF.

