### 7.3 Treatment phase

#### *Visit 2 - Day 1 (Baseline and Inclusion Visit)*

Four to six weeks later, the patients will report to the clinical center in the morning at around 8h00 ± 2h, fasting for at least 10 hours and holding their daily dose of levothyroxine and bringing with them their diary and possibly the box/bottle of the LT4 and PPI for:

- adverse events (AEs) and concomitant medications;
- body weight (BW);
- diary collection and check to verify compliance with LT4 and PPI;
- re-check of inclusion/exclusion criteria;
- urine pregnancy test (in female subjects of child bearing potential);
- blood sampling for thyroid function tests (TSH, FT4, TT4, FT3, TT3);
- serum laboratory tests: creatine phosphokinase (CPK), sex-hormone binding globulin (SHBG), ferritin, angiotensin-converting enzyme (ACE), and lipid panel (total cholesterol [TC], high-density lipoprotein cholesterol [HDL-C], low-density lipoprotein cholesterol [LDL-C], very low-density lipoprotein cholesterol [VLDL-C], triglycerides [TG]).
- Tirosint® dispensing;
- diary dispensing;
- remind the patient how to complete the diary and how to comply with the study requirements (i.e. drugs intake, study restrictions, etc.);
- fill in and send the Declaration of Inclusion.

The new onset or the worsening of clinical signs/symptoms of hypothyroidism or hyperthyroidism (e.g. palpitations) reported by the patient, if clinically significant, will have to be recorded as adverse events.

Any changes in the concomitant medications, including the PPI product and/or dose will be recorded in the CRF.

If the subject brings them, the LT4 and PPI box/bottle will be checked to verify changes from the previous visit.

Subjects who are still judged eligible will be dispensed sufficient amount of Tirosint® capsules for treatment up to Visit 3.

The date of Visit 3 will be scheduled and subjects will be asked to come to the clinical center for the next visit, holding their morning dose of LT4, and bringing with them their diary, the box of the PPI that they are on therapy with and the unused, used and partially used boxes and blisters of Tirosint®.

As far as possible, the subjects should begin taking Tirosint the same day of V2, after blood sampling has been performed. The day of first intake of Tirosint will be considered as Day 1 of the study.

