## 8 HANDLING OF MISSING AND INCOMPLETE DATA

Cases of withdrawal from the study, for any reasons, after inclusion will not be replaced. However, the withdrawn cases will be analyzed in the ITT analysis.

TSH, FT4, TT4, FT3, TT3, CPK, SHBG, ferritin, ACE level, and lipid panel (TC, HDL-C, LDL-C, VLDL-C, TG) values recorded after changes in LT4 dose will not be considered for the statistical analysis.

For analyses that require complete patient data, missing values during the treatment period will be replaced, for all primary and secondary variables, with the Last Observation Carried Forward (LOCF) technique. Imputed values will be included in the analysis set(s), but will not change the original clinical database.

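### Three protocol passages disagree on when the V2 TSH result ends participation; because V2 TSH is also the primary baseline, the raw mean change can be shifted, probably upward and by little under the written limits.

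*Protocol*

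**What the plan says.** Three places in the protocol deal with a V2 result that calls for a levothyroxine (LT4) change.

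- Section 5.3, footnote 1: "Should a patient require LT4 dose adjustment at baseline visit, the subject will be excluded". This is mandatory and has no TSH limit.
- Section 5.4: a listed reason is "if LT4 dose adjustment is required upon receipt of baseline (V2) laboratory results and before any control visit (interim or unscheduled) is performed". Again there is no TSH limit, and the list opens with "Participation may be discontinued for any of the following reasons".
- Section 6.2: "If TSH levels > 10 or < 0.01 mIU/L are measured during the baseline visit the subject will drop-out". This is mandatory and two-sided. The same section adds "The Investigator can adjust the LT4 dose for a patient with TSH levels < 10 or ≥ 0.01 mIU/L", on documented safety grounds. It does not say whether a patient changed in this way on the V2 result stays or leaves.

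At control visits section 6.2 takes a different course: "the dose will be adjusted and the subject will remain in the study". TSH values after a dose change are then not analysed (Protocol 11.3.3; SAP 7.1.1, 8 and 9.4.1).

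On timing, section 7.3 says "As far as possible, the subjects should begin taking Tirosint the same day of V2, after blood sampling has been performed". Serum goes to a central laboratory, with up to 7 days allowed for delayed shipment (section 9.1). The V2 result therefore normally arrives after the first dose, and the patient already meets the ITT definition.

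On analysis, SAP 8 says of patients who leave: "However, the withdrawn cases will be analyzed in the ITT analysis". SAP 9.4.1 runs the primary model twice, with LOCF and on original data, and does not rank the two. PP needs study completion. mITT needs V2 and V3 TSH at the same dose.

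**The concern.** In a before-after comparison, removing patients on the before value and not on the after value can shift the mean change even if the product does nothing. V2 TSH is the before value here. A V4 TSH is set aside only if the dose changed earlier, never for its own level. TSH is right-skewed, so removal on V2 is likely to take more from the upper tail and make TSH appear to rise on capsules, against the fall that the trial hopes to show.

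How many patients this touches depends on which passage a site followed. A V2 TSH of 6 judged to need a dose change leads to exclusion under footnote 1, to possible discontinuation under 5.4, and to a dose change with no stated consequence under 6.2.

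**Working it through.** **The plan's own figure.** Paired t-test, n = 48, difference 0.7, SD of differences 1.9, two-sided 0.05. The noncentrality is 0.7/1.9 × √48 = 2.55 with 47 degrees of freedom, so power is 70.5%. The stated 70% reproduces, and so does 48/0.80 = 60.

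**Assumptions for the shift.** The documents give no TSH distribution. I assumed no capsule effect, log-normal TSH with median 1.5 mIU/L, V1 limited to 0.3–4.0 (criterion I5), V2 and V4 exchangeable, and removal on V2 only. Setting A has between- and within-patient log-SDs of 0.4 and 0.606 (SD of differences 1.90). Setting B has 0.7 and 0.56 (1.91).

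**Estimators.**
- Pairs: mean of V4 − V2 among patients kept.
- V2 carried forward: removed patients count as zero change.
- Mixed model: mean V4 (kept) + slope × [mean V2 (all) − mean V2 (kept)] − mean V2 (all).

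| Removed if V2 is | Removed, A / B | Pairs, A / B | V2 carried forward, A / B | Mixed model, A / B | Log scale, pairs, A / B |
|---|---|---|---|---|---|
| > 10 or < 0.01 (written) | 0.35% / 0.63% | +0.033 / +0.052 | +0.033 / +0.052 | +0.004 / +0.015 | +0.006 / +0.008 |
| outside 0.1–6 (illustrative) | 2.4% / 3.4% | +0.125 / +0.146 | +0.122 / +0.141 | +0.018 / +0.046 | +0.030 / +0.030 |
| outside 0.3–4.0 (illustrative) | 9.2% / 12.4% | +0.256 / +0.249 | +0.232 / +0.218 | +0.046 / +0.101 | +0.064 / +0.044 |

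The mixed model on the log scale is near 0 in every row. Other log-normal choices (medians 1.5–2.0) gave +0.02 to +0.06 under the written limits. Removal above 4.5, the upper reference value quoted in section 2.1, gave +0.15 to +0.32.

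**Power at n = 48 for a true fall of 0.7, pairs analysis.** Removal also lowers the SD.
- Written limits, A: (0.7 − 0.033)/1.807 = 0.369, against 0.7/1.902 = 0.368 with no removal. Power is unchanged at about 71%.
- Outside 0.3–4.0: (0.7 − 0.256)/1.544 = 0.288 in A and (0.7 − 0.249)/1.476 = 0.306 in B. Power is about 50% and 55%.
- A variant with heavier-tailed noise (t, 4 degrees of freedom) gave shifts of +0.02 to +0.03 (written limits) and +0.08 to +0.09 (outside 0.3–4.0), and no power loss. I give it little weight on the raw scale, because exponentiated t noise has no finite mean unless truncated. It does show that the power loss is not robust.

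**Actual numbers.** SAP 4.1 reports 47 included and 45 completed, so at most two included patients left, for any reason. With assumed values:
- One patient with V2 12 who would have reached 3 at V4: (12 − 3)/47 = +0.19. Two such patients: +0.38. On the log scale one gives ln(12/3)/47 = +0.03.
- One patient with V2 0.005 who would have reached 0.5 to 1.5: −0.01 to −0.03 raw, but −ln(100)/47 to −ln(300)/47 = −0.10 to −0.12 on the log scale.

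Expected removals among 47 are 0.16 to 0.30 under the written limits (47 × 0.0035 and 47 × 0.0063), and 4.3 to 5.8 under the widest trigger (47 × 0.092 and 47 × 0.124).

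**The case against.** **The passages can be read together.** Section 6.2 can be taken to define when an adjustment is required, with 5.3 and 5.4 using that sense. The permissive opening of 5.4 covers a general list that includes death and pregnancy, so it is weak evidence of a discretionary rule. The timing clause in 5.4 matches the split in 6.2 between baseline and control visits, and 6.2 gives a reason: no same-dose comparison would be possible. Most of this stands, and the conflict is narrow. The discretionary sentence in 6.2 keeps it alive, because a change inside the limits made on the V2 result still has no agreed consequence.

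**The raw scale may not be the one used.** SAP 9.4.1 log-transforms if Shapiro-Wilk rejects normality. In log-normal samples of 48 it rejected in 98–100%. The log-scale shift under the written limits is under 1%. This stands.

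**LOCF need not use V2.** The rule covers values missing during treatment, and Protocol 11.3.3 names baseline carry-forward as a separate, optional method. SAP 8 nevertheless does not say what happens when no post-baseline value exists. An early Final Visit TSH (section 7.4) at the unchanged dose would avoid the question.

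**A stronger reading that fails.** A reader might infer that the baseline rule pushes the TSH change upward and hides a capsule benefit. The documents do not support that. The rule is two-sided, and on the log scale one very low V2 outweighs one high V2. The loss of V4 values after a V3-triggered dose change is a partial counterpart that can act the other way on original data. Power is not reduced under the written limits.

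**Conclusion.** The inconsistency is real and needs resolving; the bias is possible and, under the written limits, small. On assumed log-normal TSH the raw shift is about +0.02 to +0.06 mIU/L, 3 to 9% of the planned 0.7. It reaches about +0.2 to +0.3 only if the wording without limits is applied widely. Two non-completers fit poorly with the 4 to 6 removals that the widest use would produce, and nothing shows that either left because of V2.

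That bound has gaps. It does not cover patients excluded before being counted as included, nor a patient whose dose was changed on the V2 result but who stayed and completed, whose later values are all unusable.

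The exposed analyses are PP, mITT and any LOCF run that carries V2 forward, which keeps nearly all of the shift. The planned ITT original-data mixed model leaves at most about +0.10 raw and close to 0 on the log scale.

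**What to change.** 1. Reconcile Protocol 5.3 footnote 1, 5.4 and 6.2 into one condition and one consequence, including for a discretionary change inside the limits made on the V2 result. The clinical content is for the sponsor. As the study has ended, record how each affected patient was handled at the deviation review before analysis (SAP 6.6).
2. In SAP 8 and 9.4.1, state that V2 is not carried forward as a V4 value. Patients with no valid post-baseline TSH at the unchanged dose contribute V2 only.
3. Name the ITT original-data mixed model as the lead analysis.
4. Report the number and V2 TSH of patients removed on the V2 result.

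I would not add a run that applies the same TSH limits to V2 and V4. It removes the shift when there is no effect, but it selects on the outcome: with a true fall of 0.7 and limits at 4.5 it returned −0.47 to −0.49.

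The cost is wording in three protocol places, a few SAP sentences and a short listing. The LOCF run loses a few imputed zero-change pairs.
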